7.2. Participant Withdrawal From the Study

A participant may withdraw from the study at any time at their own request or may be withdrawn at any time at the discretion of the investigator for safety, behavioral, compliance or administrative reasons.

If a participant withdraws from the study, they may request destruction of any samples taken and not tested, and the investigator must document this in the site study records. If the participant withdraws consent for disclosure of future information, the sponsor may retain and continue to use any data collected before such a withdrawal of consent.

7.3. Lost to Follow-Up

A participant will be considered lost to follow-up if they repeatedly fail to return for scheduled visits and is unable to be contacted by the study site.

The following actions must be taken if a participant fails to return to the clinic for a required study visit:

- The site must attempt to contact the participant and reschedule the missed visit as soon as possible and counsel the participant on the importance of maintaining the assigned visit schedule and ascertain whether or not the participant wishes to and/or should continue in the study.
- Before a participant is deemed lost to follow-up, the investigator or designee must
 make every effort to regain contact with the participant (where possible, 3 telephone
 calls and, if necessary, a certified letter to the participant's last known mailing address
 or local equivalent methods). These contact attempts should be documented in the
 participant's medical record.
- Should the participant continue to be unreachable, they will be considered to have withdrawn from the study.

8. STUDY ASSESSMENTS AND PROCEDURES

8.1. Administrative and General Procedures

8.1.1. Informed Consent Process

- The investigator or his/her representative will explain the nature of the study to the participant or his/her legally authorized representative and answer all questions regarding the study.
 - Informed consent must be obtained before any study-related procedures are conducted, unless otherwise specified by the Protocol.
 - Informed consent must be obtained using the IRB/IEC-approved version in a language that is native and understandable to the participant. A template will be provided by the sponsor or its designee. The sponsor or its designee must review and acknowledge the site-specific changes to the ICF template. The ICF must include a statement that the sponsor or its designee and regulatory authorities have direct access to participant records.
 - The ICF must contain all required elements and describe the nature, scope, and possible consequences of the study in a form understandable to the study participant.
- Participants must be informed that their participation is voluntary. Participants or their legally authorized representative will be required to sign a statement of informed consent that meets the applicable requirements and regulations for the country(ies) in which the study is being conducted as well as the IRB/IEC or study center.
- The participant must be informed that his/her personal study-related data will be used by the sponsor in accordance with local data protection laws. The level of disclosure must also be explained to the participant.
- The participant must be informed that his/her medical records may be examined by Clinical Quality Assurance auditors or other authorized personnel appointed by the sponsor, by appropriate IRB/IEC members, and by inspectors from regulatory authorities.
- The medical record must include a statement that written informed consent was obtained before the participant was enrolled in the study and the date the written consent was obtained. The authorized person obtaining the informed consent must also sign the ICF.
- Participants must provide consent to the most current version of the ICF during their participation in the study.
- A copy of the ICF(s) must be provided to the participant or the participant's legally authorized representative.

A participant who is rescreened is required to sign a new ICF.

8.1.2. Screening Procedures

The screening period of a maximum of 28 days is the interval between the date of signing of informed consent and the date of randomization. The ICF must be signed before beginning any study-related assessments. Standard-of-care assessments performed on the day of consent (but before signing the ICF) do not need to be repeated solely for the purpose of screening and may be used as study data, if they meet the Protocol requirements.

Standard of care assessments that occur outside the 28-day window that are suitable for enrollment (ie, meet protocol requirements) but are not feasible to repeat may be used for determining eligibility with sponsor medical monitor approval.

During screening, each participant who signs the ICF will be allocated a unique identification number. Treatment should start within 3 days of randomization.

All participants must satisfy all the inclusion criteria and none of the exclusion criteria listed in Section 5. Signed and dated informed consent must be obtained from all participants before their entering the clinical study. Additionally, sites will complete participant enrollment forms for all participants being considered for this study. Completed enrollment forms will be submitted to the sponsor along with completely redacted (pseudonymized) supportive documentation (eg, laboratory reports, pathology reports, imaging reports, and a brief summary of the participant's disease-specific medical history) that is necessary to confirm eligibility. The PI will ultimately be responsible for ensuring participants meet eligibility criteria.

See Section 5.4 and Section 5.5 for information regarding screen failures and replacement of participants, respectively.

See Table 3 and Table 4 for the screening assessments to be performed.

8.1.3. Interactive Response Technology Procedure

Each participant is identified in the study by a unique participant number that is assigned by the IRT system when the participant is screened (ie, signs the ICF) and is retained as the primary identifier for the participant throughout their entire participation in the study.

- The participant number is unique so that each participant is numbered uniquely across the entire study.
- The investigator or designated study personnel will contact the IRT system and provide the requested identifying information for the participant to register them into the IRT system and assign a participant number.

Once assigned, the participant number must not be reused for any other participant.

All participants who fulfill all inclusion criteria and who are not barred by any of the exclusion criteria will be randomly assigned to one of the study treatment groups as defined in Section 6.1.

Randomization will be done through IRT before the participant receives any study treatment. While all inclusion and exclusion criteria need to be reviewed again before randomization, laboratory results and results of assessments obtained during the screening period or on the day of randomization may be used for determining participant eligibility for study randomization.

Additionally, the IRT will be contacted at each regular study visit to update the study drug supply. Additional details are provided in the IRT Manual.

8.1.4. Demography and Medical History

8.1.4.1. Demographics and General Medical History

Demographic variables to be recorded will include age, gender, race, and ethnic origin.

At the time of signing of the ICF, relevant medical history and current medical conditions should be recorded. The medical history, co-morbidities, and prior medications should be documented in detail, including all symptoms present at screening.

8.1.4.2. Disease Characteristics, Treatment History, and Pathology

A local pathology report indicating FL/MZL diagnosis is acceptable for determining a participant's eligibility for receiving the first study treatment. The participant will be enrolled in the study based on the local pathology report.

For each participant, suitable and sufficient tumor tissue material must be provided. A central pathologist will provide confirmation of the histological diagnosis of FL/MZL. A fresh biopsy is preferred, but an archival specimen is acceptable, preferably from the time of the last relapse. For archival specimens, surgically acquired tissue samples are preferred, but core biopsies are permitted. Bone marrow biopsies are not adequate for this purpose and should be performed only for disease staging. Refer to the Central Lab Manual for details. In cases where blocks cannot be provided, 15 unstained slides and 3 tissue curls should be provided. When tissue curls cannot be provided, 25 unstained slides should be provided.

Central pathology review is mandatory but will be retrospective; randomization is based on investigator assessment, and no changes will be made to treatment assignment for discordant results between the investigator and the central pathology laboratory. Differences will be highlighted in the final data analysis only.

Samples should be submitted within 30 days after randomization.

Examinations leading to the diagnosis of FL/MZL should be documented in the participant's source documents. This may include, for example, results of laboratory examinations, imaging results, or clinical symptoms related to FL/MZL. The assessment of the lymphoma should include disease staging. In order to reflect the participant's status at the time of screening, the standard staging systems for FL/MZL reflecting the number of sites of involvement and their relation to the diaphragm, the existence of B-symptoms, and the presence of extranodal disease, will be documented (see Appendix E and Appendix F).

See Table 3 and Table 4 for the list of all assessments required at screening. For participants with FL, the FLIPI-1 and GELF criteria assessment will also be performed and recorded in the eCRF.

8.2.1. Health Economics

Health economics parameters are not evaluated in this study.

8.2.2. Bone Marrow Biopsy and Aspirate Samples

Both bone marrow aspirate and biopsy samples are to be collected at timepoints when a bone marrow examination is indicated (see Table 3). If biopsy collection is not feasible (see Section 8.2.2.1), a bone marrow aspirate will be collected. Samples collected prior to signing the ICF may be used in lieu of collecting additional samples in discussion with the sponsor medical monitor. Please refer to the Laboratory Manual for details on sample preparation and shipment.

8.2.2.1. Bone Marrow Biopsy Sample Collection

A bone marrow biopsy is required at screening to determine if there is marrow infiltration of the underlying lymphoma. This sample will be evaluated locally unless the marrow is the only organ where disease is found.

If a bone marrow biopsy cannot be obtained, a bone marrow aspirate must be collected for local bone marrow examination to determine disease infiltration. If a bone marrow aspirate is taken in lieu of a biopsy, the sample should contain adequate volume to support MRD analysis (see Section 8.2.2.2).

Bone marrow biopsies collected as part of standard of care that are suitable for determining eligibility may be used in lieu of collecting an additional biopsy with sponsor medical monitor approval. Bone marrow aspirates must be freshly collected samples.

If the screening bone marrow examination indicates disease infiltration in the bone marrow, a bone marrow biopsy is to be repeated within 4 weeks (\pm 2 weeks) of radiologic CR for evaluation of morphologic response and MRD analysis (see Section 8.2.2.2). If CR was not achieved, a repeat bone marrow biopsy must be collected at EOT.

Results from the local bone marrow examinations must be entered in the eCRF.

8.2.2.2. Bone Marrow Aspirate Sample Collection

A bone marrow aspirate must be collected at screening and EOT and sent to the central laboratory for MRD analysis regardless of marrow involvement status at baseline. A portion of

the first draw is preferable, but the second draw can be used if there is inadequate sample volume from the first draw.

An aspirate will need to be repeated and sent for central MRD analysis at the time of radiologic CR only if marrow is involved at screening.

8.2.3. Minimal Residual Disease and Mutational Analyses in Peripheral Blood

Peripheral blood samples will be collected for MRD and mutational analyses at the timepoints listed in Table 4.

8.2.4. Radiographic and Metabolic Imaging Assessments

Radiographic assessments will be performed at the timepoints indicated below and in Table 3. Additional radiographic assessments may be performed by the investigator during the course of the study if deemed clinically necessary.

Images of the radiographic assessments will be collected and centrally stored at the sponsor's central radiology vendor. The instructions are included in the Central Imaging Manual.

All CT scans (and CT parts of a combined PET-CT, if applicable) should cover the neck, chest, abdomen, and pelvis and must be of diagnostic quality, with contrast agent, if allowable based on participant contraindications and/or supply issues. An MRI with contrast should be performed if a CT scan with contrast is contraindicated as assessed by the investigator. If both a CT with contrast and an MRI with contrast are contraindicated and/or not available due to supply issues, a CT or an MRI without contrast is acceptable as radiographic assessment methodology, but should be noted in the participant's chart and eCRF. Every effort should be made to use the same assessment methodology for a participant throughout the study duration.

The CT/MRI scan assessments will be used to serve as the baseline assessments for CT/MRI response. The PET assessments will be used to serve as the baseline assessments for PET response.

Note: PET-CT hybrid scanners may be used only if the CT produced by the scanner is of diagnostic quality (ie, allows an accurate diameter measurement and, as a guidance, a slice thickness of 2-2.5 mm is adequate; refer to the Study Manual). If using a hybrid machine for both PET and CT, the PET should be performed before the CT is performed with IV contrast, so as to not compromise PET results.

If independent CT and PET-CT scanners are used, and the participant is receiving both scans on the same day, the PET-CT must be performed before the CT with IV contrast (unless contraindicated). The CT must be of diagnostic quality (ie, allows an accurate diameter measurement and, as a guidance, a slice thickness of 2 to 2.5 mm is adequate; refer to the Study Manual). Lesion measurements and other parameters relevant for the response assessment based on the Lugano classification (Cheson et al 2014; see Appendix H) will be collected in the eCRF.

At baseline:

• PET + CT or PET + MRI scans must be performed on all participants.

During the study treatment and follow-up periods:

- Participants with negative PET scan at baseline should be followed using CT or MRI imaging. Additional PET scans may be performed at the treating investigator's discretion but are not required.
- Participants with a positive PET scan at baseline (FDG-avid lymphoma) who achieve radiologic CR during treatment should be assessed by PET scan within 4 weeks (± 2 weeks) of the CT/MRI scan, noting the CR to evaluate for metabolic response. Subsequent PET scans are not required if a confirmatory PET scan is performed during treatment; otherwise, a PET scan will need to be repeated at EOT.
- CT/MRI scans are to be performed according to the following schedule:
 - Year 1: Every 12 weeks (3 months, ± 2 weeks), including the EOT visit.
 Circumstances where scans cannot be performed at EOT (eg, due to hospitalization, hospice care, recent per-protocol scan, etc.) must be properly documented in the eCRF
 - Years 2 to 3: Every 16 weeks (4 months, \pm 2 weeks)
 - Years 4 to 6: Every 24 weeks (6 months, \pm 3 weeks)
- For CT/MRI scans reporting PD, a PET-CT or PET-MRI scan should be performed within 4 weeks (± 2 weeks) for confirmation of progression.

Response assessments using Lugano criteria (Cheson et al 2014) are to be performed each time lesions are assessed.

Participants who discontinue treatment for reasons other than disease progression will enter the efficacy follow-up period (see Section 8.9.2). Lesions must followed using the same modality and schedule as was used during the treatment period until progression of disease, initiation of new anticancer therapy, death, or withdrawal of consent.

8.2.5. Quality-of-Life Assessments

Quality-of-life assessments using the EORTC QLQ-C30, EQ-5D-5L, and FACT-Lym tools will be performed at the timepoints listed in Table 3.

8.3. Safety Assessments

Planned timepoints for all safety assessments are provided in Table 3 and Table 4.

The investigator(s) and the sponsor will review the safety data.

Safety will be evaluated by monitoring all AEs and clinically significant abnormalities identified through physical examinations, vital signs, and laboratory assessments. Such events and laboratory and AE toxicities will be graded according to NCI CTCAE v5.0 (or higher). Laboratory safety assessments will include routine monitoring of hematology and blood chemistry and tests of immunologic parameters.

Adverse events, pregnancies, concomitant medications, procedures, and hospitalizations will be recorded from signing the ICF until 90 days after the last dose of treatment or until the start of new anticancer therapy, whichever occurs first. Participants who relapse or progress and/or

prematurely discontinue the study treatment will continue to be followed for SPM throughout the study.

Adverse events and concomitant medications terms will be coded using MedDRA and a validated medication dictionary.

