5.1. Inclusion Criteria

Participants are eligible to be included in the study only if all of the following criteria apply:

- 1. Age \geq 18 years at the time of signing the ICF.
- 2. Ability to comprehend and willingness to sign a written ICF for the study.

3. Histologically confirmed Grade 1, 2, or 3a FL or histologically confirmed nodal MZL, splenic MZL, or extranodal MZL as assessed locally (Swerdlow et al 2016);

NOTE: Participants with gastric MZL and evidence of *Helicobacter pylori* must have a documented nonresponse to antibiotic therapy prior to randomization.

- 4. Willingness to avoid pregnancy or fathering children based on the criteria below.
 - a. Male participants with reproductive potential must agree to take appropriate precautions to avoid fathering children (with at least 99% certainty) from screening through 180 days (6 months) after the last dose of study treatment, even if they have undergone a successful vasectomy, and must refrain from donating sperm during this period. Permitted methods that are at least 99% effective in preventing pregnancy (see Appendix A) should be communicated to the participants and their understanding confirmed.

b. WOCBP participants:

Must commit either to abstain continuously from heterosexual sexual intercourse or agree to take appropriate precautions to avoid pregnancy (by using 2 different methods of birth control: one with at least 99% certainty and an additional effective [barrier] method) starting at least 4 weeks before taking the study treatment, while taking the study treatment, during breaks (dose interruptions), and for at least 180 days (6 months) after stopping the study treatment. Permitted methods that are at least 99% effective in preventing pregnancy and the permitted additional effective (barrier) methods (see Appendix A) should be communicated to the participants and their understanding confirmed.

Note: Because of the increased risk of venous thromboembolism, combined oral contraceptive pills are not recommended. If a participant is currently using combined oral contraception, the participant should switch to one of the effective methods listed in Appendix A. The risk of venous thromboembolism continues for 4 to 6 weeks after discontinuing combined oral contraception.

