- Must have a negative serum pregnancy test at screening (within 10-14 days of the first study drug treatment) and before the first dose on Day 1 (within 24 hours of initiating treatment with lenalidomide).
- Agree to ongoing pregnancy testing during the course of the study; weekly during
 the first month of study drug treatment, then monthly thereafter for women with
 regular menstrual cycles or every 2 weeks for women with irregular menstrual
 cycles (even if true abstinence is the chosen method of birth control) up to and
 including the EOT visit.
- Must refrain from breastfeeding and donating oocytes during the course of study and for 180 days (6 months) after the last dose of study treatment.

c. A woman not considered to be of childbearing potential as defined in Appendix A is eligible.

Note: The participants should be informed about the option of donation and cryopreservation of germ cells before the study if applicable.

5. All participants must:

- a. Have an understanding that lenalidomide could have a potential teratogenic risk.
- b. Abstain from donating blood while on study treatment and for 28 days after discontinuation of study treatment.
- c. Not share any study medications with another person.
- d. Agree to be counseled about pregnancy precautions and risk of fetal exposure.
- e. In the opinion of the investigator, be able and willing to receive adequate mandatory prophylaxis and/or therapy for thromboembolic events (eg, aspirin 70-325 mg daily or low-molecular-weight heparin). Participants unable or unwilling to take any prophylaxis are not eligible.
- f. In the opinion of the investigator, be able to understand and comply with all study-related procedures, medication use, and evaluations.
- g. In the opinion of the investigator, not have a history of noncompliance or be considered potentially unreliable and/or uncooperative.
- 6. Tumor tissue sufficient for retrospective central pathology review and correlative studies must be provided to participate in this study; a new biopsy must be performed if progression or relapse of disease is within 24 months from the initial diagnosis (POD24) to exclude transformed cases and potentially misdiagnosed cases. NOTE: A more recent biopsy is preferred if clinically feasible but if not, an archival specimen is acceptable except in cases of POD24 (refer to the Laboratory Manual).

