9.7. Pregnancy

Pregnancy, in and of itself, is not regarded as an AE unless there is suspicion that the study treatment may have interfered with the effectiveness of a contraceptive medication or method. When a pregnancy has been confirmed in a participant during maternal or paternal exposure to study treatment, the following procedures should be followed in order to ensure safety:

- The study treatment must be interrupted immediately (female participants only).
- If the female participant is no longer pregnant and meets the treatment continuation criteria within 28 days of the scheduled start of a cycle study treatment may be resumed after approval has been received from the sponsor medical monitor.
- The investigator must complete and submit the Incyte Clinical Trial Pregnancy Form to Incyte Pharmacovigilance within **24 hours** of learning of the pregnancy.

Data on fetal outcome are collected for regulatory reporting and drug safety evaluation. Follow-up should be conducted for each pregnancy to determine outcome, including spontaneous or voluntary termination, details of the birth, and the presence or absence of any birth defects, congenital abnormalities, or maternal and/or newborn complications, by following until the first well-baby visit. Pregnancy should be recorded on a Clinical Trial Pregnancy Form and reported by the investigator to the sponsor or its designee. Pregnancy follow-up information should be recorded on the same form and should include an assessment of the possible causal relationship to the sponsor's study drug to any pregnancy outcome, as well as follow-up to the first well-baby visit or the duration specified in local regulations, whichever is later. Refer to the Incyte Reference Guide for Completing the Clinical Trial Pregnancy Form or Study Reference Manual.

Any SAE occurring during pregnancy of a study participant must be recorded on the Serious Adverse Event Report Form and submitted to the sponsor or its designee.

Abnormal pregnancy outcomes (eg, spontaneous abortion, fetal death, stillbirth, congenital anomalies, or ectopic pregnancy) are considered SAEs (if occurring in the study participant) and must be reported as described in Section 9.4. If an abnormal pregnancy outcome is reported in a

study participant's partner, the event should be reported to the sponsor on the Clinical Trial Pregnancy Form.

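### Pregnancy precautions run to 180 days after the last dose, but pregnancies are recorded only to day 90 or new anticancer therapy, and Section 9.7 sets no reporting window

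*Protocol*

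**What the plan says.** **Precautions (Protocol 5.1, criterion 4).** Male participants must avoid fathering children "from screening through 180 days (6 months) after the last dose of study treatment". Women of childbearing potential (WOCBP) must abstain or use two contraceptive methods "for at least 180 days (6 months) after stopping the study treatment". They must also refrain from breastfeeding and oocyte donation "for 180 days (6 months) after the last dose of study treatment".

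**Recording (Protocol 8.3).** "Adverse events, pregnancies, concomitant medications, procedures, and hospitalizations will be recorded from signing the ICF until 90 days after the last dose of treatment". A second clause can close this window sooner: "until the start of new anticancer therapy, whichever occurs first". One sentence sets one window for several kinds of data.

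**Reporting (Protocol 9.7).** The procedures apply "When a pregnancy has been confirmed in a participant during maternal or paternal exposure to study treatment". Exposure is not given in days and there is no closing date for reporting. The first well-baby visit ends follow-up of a pregnancy already reported; it does not say which pregnancies must be reported.

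**Testing (Protocol 8.3.5.2, Table 4).** Scheduled pregnancy tests end at the safety follow-up visit, 90 days after EOT.

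**On-treatment pregnancy.** Section 7.1.1.6 requires a participant who becomes pregnant to discontinue. Section 9.7 calls for immediate interruption and allows treatment to resume, with medical monitor approval, if she is no longer pregnant and meets the continuation criteria within 28 days of the scheduled cycle start.

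**The concern.** The protocol asks participants to avoid pregnancy for 180 days after the last dose but tells sites to stop recording pregnancies at day 90, or sooner if new therapy starts. A site that follows 8.3 literally has no clear duty to record a pregnancy that begins in the second half of the precaution period. Section 9.7 does not settle the matter, because one site could read exposure as 90 days and another as 180.

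At stake is the completeness of pregnancy data in a trial where both arms receive lenalidomide. Section 6.6.2 says lenalidomide may cause fetal harm, and 9.7 says fetal outcome is collected for drug safety evaluation.

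A smaller, separate matter is that a site facing a pregnancy that ends early has two different instructions on whether treatment may restart.

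**Working it through.** The documents give no figure to reproduce. The check compares the windows and then sizes the gap.

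**1. Length of the gap.** Inputs: 180 days (5.1); 90 days or new anticancer therapy (8.3). If new therapy starts *d* days after the last dose, with *d* below 90, the unrecorded part is 180 − *d*.
- No new therapy by day 90: 180 − 90 = 90 days, 90/180 = 50%.
- New therapy on day 60 (illustrative): 120 days, 67%.
- New therapy on day 30 (illustrative): 150 days, 83%.

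These are shares of calendar time, not of pregnancies.

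**2. What other sections already cover.** For a pregnancy conceived in days 91 to 180 or after early new therapy:

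| Pregnancy | Existing route | Limit |
|---|---|---|
| Participant, abnormal outcome, no new therapy | SAE under 9.7, reportable under 9.4 to study completion | SAEs need not be actively sought after EOT |
| Participant, abnormal outcome, after new therapy | 9.4, if the investigator learns of it and considers it related | The general SAE duty has ended |
| Participant, ongoing or normal outcome | None clear | 8.3 has closed; 9.7 depends on undefined exposure |
| Partner, abnormal outcome | Under 9.7, "the event should be reported to the sponsor on the Clinical Trial Pregnancy Form" | Only if it is reported |
| Partner, ongoing or normal outcome | None clear | The 9.7 trigger mentions paternal exposure but a pregnancy in a participant |

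**3. Expected number.** Formula: WOCBP × (days / 365.25) × annual conception rate. Assumptions not in the documents: 5% to 20% of the 618 participants are WOCBP (30.9 to 123.6 women), and 1% to 5% conceive per year. Appendix A's failure rate below 1% applies to consistent, correct use, so it is not an upper bound.
- Days 91 to 180, low: 30.9 × 90/365.25 × 0.01 = 0.08.
- Days 91 to 180, high: 123.6 × 90/365.25 × 0.05 = 1.52.
- On treatment (12 × 28 = 336 days), low: 30.9 × 336/365.25 × 0.01 = 0.28.
- On treatment, high: 123.6 × 336/365.25 × 0.05 = 5.69.

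The 7.1.1.6 and 9.7 conflict concerns an unknown fraction of the on-treatment figure. Partner pregnancies are additional and cannot be estimated from the documents.

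**4. Where a question could be asked.** Survival contacts are every 12 weeks from EOT, ± 4 weeks (8.9.3). The second is nominally day 168 from EOT, window 140 to 196. If EOT falls on the last-dose day, a contact at day 140 leaves 180 − 140 = 40 days unasked. For a completer, the last lenalidomide dose is Cycle 12 Day 21 and EOT is Day 28, so day 140 from EOT is day 147 from the last dose, leaving 180 − 147 = 33 days. The question should therefore go to the first contact on or after day 180 from the last dose.

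**The case against.** **The 90 days was deliberate.** This stands as an account of intent. Appendix J (Amendment 2-EU) ties the period to tafasitamab's 16.9-day half-life (90/16.9 = 5.3 half-lives), in an amendment answering regulatory requests. That reasoning set one period for AEs, medications, pregnancies and other data together and does not mention the 180-day precautions.

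**Precautions may reasonably outlast recording.** This also stands. A reader might infer that 180 days is the protocol's stated period of fetal risk and that 8.3 contradicts it. The documents do not support that: 5.1 sets a precaution period, no section links days 91 to 180 specifically to lenalidomide, and exclusion criterion 1 uses 90 days for breastfeeding in Japan. What remains is a mismatch worth closing.

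**Section 9.7 has no cutoff, so it may already reach day 180.** Possible, but it turns on a term the protocol leaves undefined, and the only recording limit stated in days is 90. The Study Reference Manual, the guide to the pregnancy form and the pregnancy prevention plan may define exposure; they were not available for this review.

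**The numbers are too small for a rate.** Agreed. The case rests on completeness of individual reports, not on estimating a proportion.

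**Survival contacts.** A reader might infer that they collect only survival and new therapy. The text of 8.9.3 has gaps, and 8.3 also follows second primary malignancies throughout the study, so that cannot be concluded.

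**Conclusion.** The mismatch is real on the current text. Following 8.3 as written leaves at least half of the 180-day precaution period without a clear duty to record ongoing or normal-outcome pregnancies and partner pregnancies, and 9.7 does not resolve it. The size is small: about 0.1 to 1.5 participant pregnancies in days 91 to 180, wholly dependent on the assumed WOCBP share and conception rate, plus partner pregnancies that cannot be sized.

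Two stronger readings fail. Late abnormal outcomes would not all go unreported, because in participants they are SAEs and in partners they go on the pregnancy form if reported. Nor does the difference between 7.1.1.6 and 9.7 permit dosing during pregnancy; they differ only on whether treatment may restart after a pregnancy that ends early.

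Efficacy, alpha and power are unaffected. This is a cheap improvement in safety recording and does not bear on the validity of the trial.

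**What to change.** 1. **Section 8.3.** Take pregnancies out of the 90-day sentence and add: *Pregnancies in participants and in partners of male participants with an estimated conception date from ICF signing until 180 days after the last dose will be recorded whenever the site learns of them, regardless of new anticancer therapy.*
2. **Section 9.7.** Change the trigger to a pregnancy in a participant, or in the partner of a male participant, with an estimated conception date from first dose until 180 days after the last dose, whenever it is confirmed. Using the conception date matters: a window on confirmation would miss a day-170 conception confirmed on day 190.
3. **Follow-up.** Ask WOCBP and male participants one pregnancy question at the first existing efficacy or survival contact on or after 180 days from the last dose.
4. **Sections 7.1.1.6 and 9.7.** Either make 7.1.1.6 refer to 9.7, so that treatment stops immediately and is permanently discontinued unless the resumption conditions are met, or delete the resumption bullet in 9.7. The choice is the sponsor's.

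**Cost.** Wording at the next amendment and one added question, with no new visits or tests. The question needs direct contact with the participant, whereas 8.9.3 allows survival status to come from records. After the safety follow-up visit, capture relies on self-report. Partner data need the partner's consent.
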